8.1.8. Photographs of Skin Lesions

Photographs of selected HS lesions will be taken at a subset of study sites in participants who provide additional consent. Consult the Trial Center File for photography instructions.

8.2. Safety Assessments

Details regarding the DMC are provided in Committees Structure in Section 9.6, Data Monitoring Committee.

Adverse events will be reported and followed by the investigator as specified in Section 8.3, Adverse Events and Serious Adverse Events and Appendix 6 (Section 10.6), Adverse Events: Definitions and Procedures for Recording, Evaluating, Follow-Up, and Reporting.

Any clinically relevant changes occurring during the study must be recorded on the Adverse Event section of the eCRF.

Any clinically significant abnormalities persisting at the end of the study/early withdrawal will be followed by the investigator until resolution or until a clinically stable condition is reached.

The study will include the following evaluations of safety and tolerability according to the time points provided in the Schedule of Activities (Section 1.3):

8.2.1. Physical Examination

Physical Examination

Physical examinations will be performed by the investigator or designated physician, nurse practitioner or physician assistant as specified in the Schedule of Activities (Section 1.3). Any new, clinically significant finding (in the opinion of the investigator) must be captured as an AE. In addition, resolution of any abnormal findings during the study will be noted in the source document and in the eCRF.

Height and Weight

Height and weight will be measured as specified in the Schedule of Activities (Section 1.3). Participants will be instructed to remove shoes and outdoor apparel and gear prior to these measurements.

Waist Circumference

Waist Circumference will be measured as specified in the Schedule of Activities (Section 1.3).

8.2.2. Vital Signs

Vital signs (including temperature, pulse/heart rate, respiratory rate, and blood pressure) will be obtained before and approximately every 30 minutes during every IV infusion, and at approximately 30 minutes after completion of the final IV infusion.

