- k. For all visits where study intervention will be administrated, one blood sample should be collected prior to study intervention administration for evaluation of serum concentration of guselkumab and/or antibodies to guselkumab. In addition, for IV infusion-related visits (ie, Weeks 0, 4, and 8), another blood draw should be taken approximately 60 minutes after completion of the infusion for serum concentration of guselkumab.
- 1. Participants who terminated study participation early should have a safety follow-up visit approximately 12 weeks after their last administration of study intervention. Serum samples should be collected at this visit for serum drug concentration measurement and antibody to drug assessment.

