6. STUDY INTERVENTION

6.1. Study Interventions Administered

All participants will receive 1 IV infusion at Weeks 0, 4, and 8 (either active or placebo).

All participants will receive 2 SC injections at each visit (either active, active and placebo, or placebo) every 4 weeks from Weeks 0 to 36.

Intravenous study intervention should be administered over a period of not less than 1 hour, and not more than 2 hours. The infusion should be completed within 6 hours of preparation.

Since 2 SC injections will be administered at each administration visit, each SC injection should be given at a different location of the body.

Detailed instructions on the administration of IV and SC study intervention will be provided in the Site Investigational Product (IP) Binder.

Study intervention administration must be captured in the source documents and the electronic case report form (eCRF).

Guselkumab and placebo will be manufactured and provided under the responsibility of the sponsor. Refer to the IB for a list of excipients.

For details on rescue medications, refer to Section 6.5.1. For a definition of study intervention overdose, refer to Section 8.4, Treatment of Overdose.

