8.2.9. Adverse Events Temporarily Related to Infusion

Any AE that occurs during or within 1 hour after the IV infusion of study intervention will be carefully evaluated. Minor infusion-related AEs may be managed by slowing the rate of the IV infusion and/or treating with antihistamines and/or acetaminophen (paracetamol) as clinically indicated. If an IV infusion of study intervention is stopped because of an AE that, in the opinion of the investigator, is not severe or does not result in a SAE, the infusion may be restarted with caution.

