9.4.3. Safety Analyses

Safety data, including but not limited to, AEs, SAEs, infections, serious infections, mortality, changes in laboratory assessments, and changes in vital signs will be summarized. Intervention-emergent AEs will be summarized by treatment group and Medical Dictionary for Regulatory

Activities (MedDRA) system organ class and preferred terms. Details will be specified in the SAP.

Safety Definition

Injection-Site Reactions

An injection-site reaction is any unfavorable or unintended sign that occurs at an injection-site and will be recorded as an AE. Detailed instructions for the evaluation of injection-site reactions are in the Trial Center File.

Adverse Events

The verbatim terms used in the eCRF by investigators to identify AEs will be coded using the MedDRA. Intervention-emergent AEs are AEs with onset during the intervention period or that are a consequence of a pre-existing condition that has worsened since baseline. All intervention-emergent AEs will be included in the analysis. For each AE, the percentage of participants who experience at least 1 occurrence of the given event will be summarized by intervention group. In addition, comparisons between intervention groups will be provided if appropriate.

Summaries, listings, datasets, or participant narratives may be provided, as appropriate, for those participants who die, who discontinue intervention due to an AE, or who experience a severe or a SAE.

The following analyses will also be used to assess the safety of participants in the study:

- The incidence and type of AEs.
- The incidence and type of SAEs.
- The incidence and type of infections.
- The incidence and type of reasonably related AEs.
- The incidence and type of injection-site reactions.
- The incidence and type of AEs temporally associated with infusion (defined as an AE that occurred on the same day of infusion, with a start time during infusion or ≤ 60 minutes after the end of infusion).
- The laboratory parameters and change from baseline in selected laboratory parameters (hematology and chemistry).
- The incidence of abnormal laboratory parameters (hematology and chemistry).

Listings of participants with SAEs and anaphylactic reaction/serum sickness reactions will also be provided. All safety analyses will be based on the population of participants who received at least 1 administration of study intervention; participants will be summarized by the intervention they received.

Clinical Laboratory Tests

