6.1. Adverse Events

The verbatim terms used in the CRF by investigators to identify adverse events will be coded using the Medical Dictionary for Regulatory Activities (MedDRA). Any AE starting at or after the initial administration of study agent through the end of the trial is considered to be treatment emergent. If the event occurs on the day of the initial administration of study agent, and either event time or time of administration are missing, then the event will be assumed to be treatment emergent. If the event date is recorded as partial or completely missing, then the event will be considered to be treatment emergent unless it is known to be prior to the first administration of study agent based on partial onset date or resolution date. All reported treatment-emergent adverse events will be included in the analysis.

Infusion Reactions

A comprehensive clinical review of all AEs that occurred on the same day of infusion, with a start time during infusion or ≤ 60 minutes after the end of IV infusion of study agent (AEs temporally related to infusion), with the exception of laboratory abnormalities, will be performed to identify the occurrence of potential infusion reactions. Specifically, the reported AEs temporally related to infusion will be reviewed to identify participants with a contemporaneous constellation of AE terms that are consistent with the signs or symptoms that typically occur during hypersensitivity reactions or cytokine release syndromes (eg, anaphylaxis, fever, chills, rigors, hypotension,

hypertension, bronchospasm, laryngospasm, wheezing, dyspnea, syncope, pre-syncope, urticaria, angioedema, generalized pruritus, flushing, rash, and nausea), to identify all participants with potential infusion reactions.

Injection-site Reactions

A study intervention injection-site reaction is any adverse reaction at an SC study intervention injection-site. The injection sites will be evaluated for reactions and any injection-site reactions will be recorded as an AE.

Any unfavorable or unintended sign that occurs at the injection (infusion) site is an injection site reaction and will be recorded as an injection site reaction by the investigator on the eCRF

Infection

An infection is defined as any AE that was recorded as an infection by the investigator on the eCRF.

The following analyses will also be used to assess the safety of participants in the study:

- The incidence and type of AEs.
- The incidence and type of SAEs.

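### Post-infusion vital signs are scheduled only after the last IV infusion (Week 8), although infusion-related AEs are counted to 60 minutes after all three

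*Protocol*

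**What the plan says.** Protocol 8.2.2 times vital signs (temperature, pulse, respiratory rate and blood pressure) around infusions in one sentence: before and at roughly half-hour intervals during every infusion, and then "at approximately 30 minutes after completion of the final IV infusion". Protocol 6.1 gives every participant, in all three arms, one infusion at each of Weeks 0, 4 and 8, "administered over a period of not less than 1 hour, and not more than 2 hours".

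The safety window is wider than that vital-sign schedule. Protocol 8.2.9 states: "Any AE that occurs during or within 1 hour after the IV infusion of study intervention will be carefully evaluated". Protocol 9.4.3 defines AEs temporally associated with infusion as same-day events "with a start time during infusion or ≤ 60 minutes after the end of infusion", and SAP 6.1 uses the same definition. SAP 6.1 then has these AEs reviewed for combinations of terms that suggest an infusion reaction. Its examples begin "anaphylaxis, fever, chills, rigors, hypotension" and go on to include hypertension.

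**The concern.** Within one sentence, Section 8.2.2 applies the readings before and during infusion to every infusion and the reading afterwards to the final one. With one infusion per visit, the final one is at Week 8. Sites that follow the text literally will take no scheduled vital signs after the Week 0 and Week 4 infusions end.

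The plan nevertheless counts events over the same 60 minutes after all three. Fever, hypotension and hypertension are recognised by measurement, and without symptoms they are usually found only if someone measures. Ascertainment of such events is therefore weaker after the first two infusions than after the third.

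The placement also gives up clinical value. A reading after Week 8 cannot inform a later infusion because none follows, whereas readings after Weeks 0 and 4 could. Initial safety and tolerability are part of the primary objective (Protocol 3). The highest earlier single IV dose the protocol reports is 987 mg, in one participant (Protocol 2.2), against 1200 mg given three times here. Protocol 2.3 mentions a Crohn's disease program using the same 1200 mg regimen, but describes it as ongoing and reports no safety results from it.

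**Working it through.** The plan states no figure to reproduce. The check is a cross-reading followed by a count.

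**Step 1: is a post-infusion reading scheduled elsewhere?**

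- Schedule of Activities (Protocol 1.3): vital signs are marked by visit, including Weeks 0, 4 and 8. Footnote c places procedures before dosing unless otherwise indicated, so these marks add nothing after the infusion.
- Footnote k: the only timed post-infusion procedure at all three visits is for PK, "another blood draw should be taken approximately 60 minutes after completion of the infusion for serum concentration of guselkumab". No vital signs are attached to it.
- Protocol 8.2.8 and 8.2.9: observation for allergic symptoms and evaluation of AEs, with no vital-sign time point.
- SAP 6.3: refers back to the protocol schedule.

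Scheduled post-infusion readings per participant are therefore 0 at Week 0, 0 at Week 4 and 1 at Week 8.

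**Step 2: count of infusions.** Inputs are 60 participants per arm and 180 in total (Protocol 9.2), with 3 infusions each (Protocol 6.1). Full enrolment and complete infusion dosing are assumed.

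| | Planned infusions | With a post-infusion reading | Without |
|---|---|---|---|
| All arms | 180 × 3 = 540 | 180 × 1 = 180 (180/540 = 33%) | 180 × 2 = 360 |
| Each arm | 60 × 3 = 180 | 60 × 1 = 60 | 60 × 2 = 120 |

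Only Group 1 receives guselkumab by IV, so 120 of the infusions without a reading are 1200 mg guselkumab infusions.

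**Step 3: share of the AE window without scheduled vital signs at Weeks 0 and 4.** The window is the infusion time plus 60 minutes.

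- 1-hour infusion: 60/(60 + 60) = 50%.
- 2-hour infusion: 60/(120 + 60) = 33%.

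These are shares of clock time, not of events missed. The documents give no basis for estimating how many events would be missed.

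**Step 4: after the change.** Scheduled post-infusion readings rise from 1 to 3 per participant: from 60 to 180 per arm and from 180 to 540 overall. That is 2 × 180 = 360 additional sets.

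**The case against.** The strongest reply is that no planned result depends on this reading. AE tables count participants with at least one event by treatment group (SAP 6.1), no analysis compares the first infusion with the third, and vital signs are summarised descriptively (SAP 6.3). All arms have the same schedule under blinded, placebo-matched dosing, so the comparison between arms is not biased. This stands, and it is why the point is a recommended improvement rather than an essential correction.

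A second reply is that the plan acts mainly on symptomatic events. The hypotension criterion for stopping treatment requires symptoms (Protocol 7.1, 8.2.8), symptoms would prompt a measurement, and SAP 6.1 looks for several terms occurring together rather than one isolated reading. Staff must observe participants after every infusion, and the last reading during an infusion may fall close to its end. This also largely stands. What remains are mild or silent changes that an investigator might have judged clinically relevant and recorded as an AE. Nothing in the protocol forbids extra readings, though nothing schedules them either. The detailed IV instructions are in a site binder that is not among the documents, so actual site practice is unknown.

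A third reply is that the pooled count of 360 overstates the matter, since only one arm receives guselkumab by IV. That is fair. For guselkumab exposure the relevant figure is 120 of 180, which is the same proportion.

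Finally, the sponsor may have meant the end of each visit's infusion. The wording does not say that, and the contrast with every infusion in the same sentence points the other way. The same edit would resolve the ambiguity.

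**Conclusion.** The concern holds. As written, the protocol schedules no vital signs in the hour after two of each participant's three infusions, although AEs are evaluated and counted over that hour for all three. This rests on reading the final infusion as Week 8, which follows from one infusion per visit. The counts rest on full enrolment and on all infusions being given.

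The consequence is modest. Detection of mild or asymptomatic temperature and blood-pressure changes is less complete after the first two infusions, and no scheduled post-infusion reading is available while it could still inform a later IV dose. Efficacy analyses and the between-arm safety comparison are not compromised. Because the regimen exceeds the highest single IV dose previously reported and safety is a primary objective, the change is worth making.

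**What to change.** In Protocol 8.2.2, require the reading about 30 minutes after completion of each IV infusion instead of only the final one.

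The added burden is two routine sets of vital signs per participant, one at Week 0 and one at Week 4, or 360 in total. They can be taken while the participant is already due on site for the PK draw. Sample size, endpoints and analyses do not change.

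The wording change is small but needs a formal amendment, with ethics committee approval before it is implemented (Protocol 10.5), so it is best combined with other changes. Infusions given before it takes effect cannot be recovered.

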8.2.3. Electrocardiogram

A single 12-lead electrocardiogram (ECG) will be performed during screening to serve as a baseline reference for comparison, should a subsequent cardiovascular related safety event occur.

8.2.4. Clinical Safety Laboratory Assessments

Blood samples for serum chemistry and hematology will be collected as noted in Section 8 and Appendix 3 (Section 10.3). The investigator must review the laboratory results, document this review, and record any clinically relevant changes occurring during the study in the AE section of the eCRF. The laboratory reports must be filed with the source documents.

The tests that will be performed by the central laboratory unless otherwise specified or approved by the medical monitor are specified in Appendix 3 (Section 10.3), Clinical Laboratory Tests.

Female participants of childbearing potential will undergo a urine pregnancy test at screening, before each study intervention administration, and at the Week 48 or early termination visit.

A medical monitor or delegate and the clinical site will be notified if prespecified abnormal laboratory values defined in the laboratory manual are identified in any participant during the conduct of the study.

8.2.5. Columbia-Suicide Severity Rating Scale (C-SSRS)

The C-SSRS defines 5 subtypes of suicidal ideation and 4 possible suicidal behaviors, as well as non-suicidal self-injurious behavior and completed suicide. It will be used as a screening tool to prospectively evaluate suicidal ideation and behavior in this study, as part of a comprehensive evaluation of safety. The C-SSRS is an investigator-administered questionnaire. ^{13,15}Two versions of it will be used in this study: the 'Baseline/Screening' version of the C-SSRS (see Appendix 15, [Section 10.15])will be conducted during the screening visit and the 'Since Last Visit' version of the C-SSRS (see Appendix 16, [Section 10.16]) will be completed at all other visits through the end of the study.

The investigator or trained study-site personnel will interview the participant and complete the C-SSRS. The C-SSRS will be provided in the local languages in accordance with local guidelines.

At screening and after obtaining informed consent, the C-SSRS will be the first assessment performed, before any other study procedure. At all subsequent visits, the C-SSRS will be performed according to the Schedule of Activities (Section 1.3) and should be performed before any tests, procedures, or other consultations, with the exception of the urine pregnancy test, to prevent influencing participant perceptions. Participants will be interviewed by the investigator or trained study-site personnel in a private, quiet place.

At the conclusion of each assessment, the trained personnel administering the C-SSRS will determine the level of suicidal ideation or behavior, if any. They will then determine the next course of action if any level of suicidal ideation or behavior is reported. The participant should not be released from the site until the C-SSRS has been reviewed by the investigator and the participant's risk has been assessed and follow-up determined, as appropriate.

At screening (within the last 6 months) and Week 0, participants with a C-SSRS rating of Suicidal Ideation with Intention to Act ("Ideation level 4"), Suicidal Ideation with Specific Plan and Intent ("Ideation level 5"), or suicidal behavior (actual suicide attempt, interrupted suicide attempt, aborted suicide attempt, or preparatory behaviors for making a suicide attempt), must be determined to not be at risk by the investigator based on an evaluation by a mental health professional (eg, psychiatrist, psychologist, or appropriately trained social worker or nurse) in order to be randomized.

Participants with C-SSRS ratings of Wish to be Dead ("Ideation level 1"), Non-Specific Active Suicidal Thoughts ("Ideation level 2"), Active Suicidal Ideation with Any Methods (Not Plan) without Intent to Act ("Ideation level 3") or non-suicidal self-injurious behavior must be determined not to be at risk by the investigator in order to be randomized. Any questions

regarding eligibility of such participants should be discussed with the medical monitor or designee.

For each assessment after Week 0, the following actions should be taken, if applicable:

- No suicidal ideation or behaviors (including self-injurious behavior without suicidal intent): No further action is needed.
- Suicidal ideation levels 1-3 or non-suicidal self-injurious behavior: Participant risk is assessed by the investigator.
- Suicidal ideation levels 4 or 5 or any suicidal behavior: Participant risk assessed and referral to a mental health professional.

Interruption or the discontinuation of study intervention should be considered for any participant who reports Suicidal Ideation with Intention to Act ("Ideation level 4"), Suicidal Ideation with Specific Plan and Intent ("Ideation level 5"), or suicidal behavior (actual suicide attempt, interrupted suicide attempt, aborted suicide attempt, or preparatory behaviors for making a suicide attempt) on a post-baseline C-SSRS assessment and who is deemed to be at risk by the investigator based upon evaluation by a mental health professional. If a participant can be adequately treated with psychotherapy and/or pharmacotherapy then the participant, at the discretion of the investigator, may be continued with treatment if agreed to by the medical monitor or designee. Discussion of such participants with the medical monitor or designee is required (see Section 7.1, Discontinuation of Study Intervention).

Any C-SSRS finding, which in the opinion of the investigator is new or considered to be a worsening and clinically significant, should be reported on the AE eCRF (see Appendix 6 [Section 10.6], Adverse Events: Definitions and Procedures for Recording, Evaluating, Follow-up, and Reporting).

8.2.6. Immunogenicity Assessments

Anti-guselkumab antibodies will be evaluated in serum samples collected from all participants according to the Schedule of Activities (Section 1.3). Additionally, serum samples should also be collected at the final visit or at the Early Termination Visit from participants who are discontinued from intervention or withdrawn from the study. These samples will be tested by the sponsor or sponsor's designee.

Serum samples will be screened for antibodies binding to guselkumab and the titer of confirmed positive samples will be reported as applicable. Other analyses may be performed to further characterize the immunogenicity of guselkumab.

Samples collected for immunogenicity analyses may additionally be used to evaluate safety or efficacy aspects that address concerns arising during or after the study period. Genetic analyses will not be performed on these serum samples. Participant confidentiality will be maintained.

Evaluations

At visits where antibodies to study intervention will be evaluated in addition to serum concentration of study intervention, 1 venous blood sample of sufficient volume should be collected. Each serum sample will be divided into 3 aliquots (1 each for serum concentration of study intervention, antibodies to study intervention, and a back-up).

Immunogenicity Analytical Procedures

The detection and characterization of anti-guselkumab antibodies will be performed using a validated assay method by or under the supervision of the sponsor. All samples collected for detection of anti-guselkumab antibodies will also be evaluated for guselkumab serum concentration to enable interpretation of the antibody data.

